7.6. Examination of Subgroups

As exploratory analyses, subgroup analysis (e.g. age, sex, HRG, HPV, primary tumor site, etc) for selective efficacy endpoints will be conducted (Section 8.2.4).

8. STATISTICAL ANALYSIS

8.1. Study Population Data

8.1.1. Subject Disposition

Subject disposition will be summarized by randomized treatment group and overall for All Screened Subjects. The number and percentage of subjects in the Full Analysis Set, the Per Protocol Analysis Set, the Safety Analysis Set, the Pharmacokinetics Analysis Set, and the PRO Analysis Sets will be presented. Subject status (ongoing, if any, and discontinued from study treatment) and the reasons for discontinuation (as reported on CRF EOT page) will be summarized in this table. All percentages, except those for All Screened Subjects, will be based on the Full Analysis Set. A listing will present data relevant to subject disposition.

8.1.2. Protocol Deviations

Protocol deviations collected by clinical team, as well as those identified in the CRF data will be provided in a listing.

Protocol deviations will be finalized prior to database lock.

8.1.3. Demographic and Baseline Characteristics

Demographic and baseline characteristics will be summarized by treatment group and overall for the FAS as well as the HRG-high stratum of the FAS, Per-Protocol analysis set (if substantial differences such as >5% as compared to the FAS), and Safety Analysis Set. If two sets of subjects are identical to each other, analysis will only be performed once.

Demographic characteristics consist of age, gender, race, and ethnicity. A subject's age in years is calculated using the informed consent date and the birth date $[(\text{consent date} - \text{birthdate})/365.25]$. Age will additionally be categorized as (≤ 65 , > 65) for reporting purposes.

Baseline characteristics consist of height, weight, tumor stage at study entry, tumor grade, prior systemic cancer therapy (Yes or No), prior radiation therapy (Yes or No), time from diagnosis of SCCHN to study treatment, histology subtype, HRG value, HPV Status, tobacco history (cigarettes and cigars), ECOG performance status, and ECG findings at baseline.

Individual subject listings of all demographic, baseline characteristics, SCCHN cancer history, medical and surgical history including prior cancer history and prior cancer surgery, and prior cancer therapy will be provided.

8.2. Efficacy Analyses

Efficacy analyses will be performed on the FAS and per-protocol analysis set as well as HRG strata. Subjects will be analyzed according to the treatment assigned at randomization.

8.2.1. Analysis of Primary Efficacy Variables

The primary efficacy endpoint is PFS as defined in Section 5.1.1 of this SAP. Progression will be determined based on the investigators' assessment.

The primary efficacy analysis will be the comparison of PFS between the patritumab arm and the control arm in HRG-high stratum of the FAS using the stratified log-rank test. For a description of the handling of censored data for efficacy endpoint PFS, see Section 5.1 above.

The testing hypotheses to compare PFS for the patritumab arm versus the control arm will be performed in two sequential steps (Freidlin 2012 et al). In step 1, the null hypothesis that PFS is the same for both arms in the HRG high stratum of FAS is tested at the one-sided 0.10 significance level. If this test in step 1 does not reject the null hypothesis, then in step 2A, the null hypothesis that PFS is the same for both arms in the FAS (HRG high stratum + low stratum) will be tested at the one-sided 0.05 significance level. If the test in step 1 is rejected, then in step 2B, the two-sided 80% confidence interval (CI) for hazard ratio (HR) of PFS in the HRG low stratum of the FAS will be estimated.

The comparison of PFS between the patritumab arm and the control arm will be performed using a log-rank test stratified by the stratification factors.

Hypothesis testing for superiority with regard to PFS will be performed with a 1-sided hypotheses setting.

Suppose that $S_A(t)$ and $S_P(t)$ are the cumulative survival functions for PFS in patritumab and control treatment groups, respectively. The null hypothesis H_0 with PFS:

$$H_0: S_A(t) = S_P(t) \text{ for all } t \geq 0 \text{ (identical survival functions for both groups)}$$

will be tested against the 1-sided alternative hypothesis H_A :

$$H_A: S_A(t) \geq S_P(t) \text{ for all } t \geq 0 \text{ and } S_A(t) > S_P(t) \text{ for at least some } t > 0$$

(improvement in PFS in the patritumab group over the control group)

The stratified log-rank test will be conducted using SAS PROC LIFETEST where the STRATA statement will include the treatment group and the stratification factors [HPV (positive vs other) and HRG (high vs. low, only for the FAS) at randomization]. The 1-sided p-value will therefore be obtained and H_0 will be rejected if p-value \leq the pre-specified 1-sided alpha.

The Kaplan-Meier product-limit method will be used to estimate the distribution of PFS for the patritumab arm versus the control arm. The median PFS for each treatment group will be based on the Kaplan-Meier estimate and the 95% confidence intervals for each treatment group will be calculated using the method of Brookmeyer and Crowley. The

median and confidence interval will be reported in months, and days will be converted to months by dividing by 30.4. The corresponding Kaplan-Meier curves will also be presented.

Estimates of HR between 2 arms along with their two-sided 80% and 95% CIs will be calculated using stratified Cox proportional hazards regression model. SAS PROC PHREG with the treatment group as the model covariate and stratification factors [HPV (positive vs other) and HRG (high vs. low) at randomization] as the STRATA variables will be used for this model. The Efron's method will be used to handle ties.

The above analysis for PFS will be repeated for the per-protocol analysis set. A separate analysis which includes clinical progression as a PFS event will be done as a sensitivity analysis.

8.2.2. Analysis of Secondary Efficacy Variables

8.2.2.1. Overall Survival

OS will be analyzed in the same manner as for PFS. Estimates of HR between the patritumab arm and the control arm along with their two-sided 80% and 95% CIs will be calculated using stratified Cox proportional hazards regression model. SAS PROC PHREG with the treatment group as the model covariate and stratification factors at randomization as the STRATA variables will be used for this model. The Efron's method will be used to handle ties. The corresponding Kaplan-Meier curves will also be presented.

8.2.2.2. Objective Response Rate

The number and the percentage of the subjects with the best overall tumor responses of either CR or PR (the objective response) will be tabulated by treatment group. Percentages will be calculated based on the number of subjects in the respective treatment group. The differences in the ORR between the control arm and patritumab arm will be presented along with two-sided 80% and 95% CIs based on the Wilson's score method with continuity correction.

In addition, the percent change from baseline will be calculated for the sum of longest diameters (LD) for all target lesions at each post-treatment evaluation for each subject, if applicable. The percent change in the sum of longest diameters from baseline in target lesions will be summarized by treatment group and assessment time with descriptive statistics; the largest decrease from baseline will also be summarized and displayed in the waterfall plots.

Best overall response and tumor assessments (target lesions, non-target lesions and overall) will be listed for all subjects in the Full Analysis Set. Percent change from the nadir (i.e., minimum sum of LD, including baseline, if that is the minimum value, up to the preceding tumor assessment) will be presented in the listing for target lesions.

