The primary analysis is PFS comparison between the patritumab arm and the control arm in HRG-high stratum of the FAS. The testing hypotheses to compare PFS between the patritumab arm versus the control arm will be performed in two steps. In step 1, the null hypothesis that PFS is the same for both arms in the HRG high stratum of FAS is tested at the one sided 0.10 significance level. If this test in step 1 does not reject the null hypothesis, then in step 2A, the null hypothesis that PFS is the same for both arms in the FAS will be tested at the one-sided 0.05 significance level. If the test in step 1 is rejected, then in step 2B, the two-sided 80% confidence interval (CI) for hazard ratio (HR) of PFS in the HRG low stratum of the FAS will be estimated.

The comparison of PFS between the patritumab arm and the control arm will be performed using a log-rank test stratified by the stratification factors in both the FAS and the HRG high stratum of FAS. The stratification factors include HPV (positive vs other) and HRG (high vs. low, only for the FAS) at randomization. Kaplan-Meier methods will be used to calculate median PFS and CIs and generate Kaplan-Meier curves for PFS. Estimates of HR between 2 arms along with their two-sided 80% and 95% CIs will be calculated using stratified Cox's proportional hazards regression model. The model will include the treatment group as a covariate and the stratification factors used at randomization as strata.

The above analysis for PFS will also be performed in the per-protocol analysis set.

Statistical Analysis for the Secondary Endpoints: Secondary efficacy variables include OS and ORR (CR and PR). Overall survival is defined from the date of randomization to death due to any cause and will be analyzed in the same manner as PFS. Subjects who are alive at the time of data cut off for overall survival analysis will be censored at the last contact date at which the subject is known to be alive. ORR is defined as the proportion of subjects with the best overall response of CR or PR regardless of whether it is confirmed or unconfirmed. The differences in the ORR between the control arm and patritumab arm will be presented along with two-sided 80% and 95% CIs based on the Wilson's score method with continuity correction. These analyses will be done using the FAS for HRG high and low strata.

Safety data will be analyzed descriptively.

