7.1. Adjustment for Covariates

No other covariate adjustments will be applied for primary and secondary efficacy analyses, except for the stratification variables if applicable. The PRO analyses will use baseline values of the dependent variable as a covariate in a mixed model.

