8.2.4.2. Subgroup Analysis

The subgroup analyses for PFS and OS specified in Section **Error! Reference source not found.** and Section **Error! Reference source not found.** will be performed for the subgroups below if data warrants:

- Age (≤ 65 , > 65 yrs)
- Sex (Female, Male)
- Race (White, Non-white)
- HPV status (Positive, Negative)
- HRG subgroups (alternative cutoffs)
- Primary tumor site (oral cavity, oropharynx, hypopharynx, and larynx)
- ECOG performance status (0, 1)
- Platinum-based therapy (cisplatin carboplatin; n.b., subjects treated with both will be excluded)
- Tumor grade (well- or moderately differentiated, poorly differentiated)
- Previous treatment (neoadjuvant chemotherapy, radiochemotherapy)
- Baseline FACT-H&N total score (\leq median, $>$ median)

A Cox proportional hazards regression with treatment as the only covariate will be applied. Forest plots will be presented for both PFS and OS.

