8.7. Other Variables Analyses

8.7.1. Patient Reported Outcomes

The FACT-H&N total score (FACT-G +disease specific subscale score), the FACT-H&N individual subscale scores (Physical Well Being (PWB), Social Well Being (SWB), Emotional Well Being (EWB), Functional Well Being (FWB)), FACT-G total score, and the FACT-H&N FHNSI score and change from baseline will be summarized by visit and treatment group using the FACT-H&N Analysis Set.

For each post-baseline assessment:

- Observed range; Mean (SD) by treatment group (overall, HPV+ and HPV-) will be reported for each of the scores listed above.
- The entire Cumulative Distribution Function (CDF) of change from baseline on FACT-G, FACT-H&N FHNSI and FACT-H&N total score will be presented as a continuous plot of the change from baseline on the X-axis and the cumulative percent of subjects experiencing that change on the Y-axis for each treatment group.

Change from baseline in the FACT-H&N total score (FACT-G +disease specific subscale score), the FACT-H&N individual subscale scores, FACT-G total score, and the FACT-H&N FHNSI score, will also be evaluated using mixed longitudinal modeling for the FACT-H&N Analysis Set. The model will include treatment, time, treatment-by-time interaction, and baseline as fixed effects. The unstructured option for the REPEATED statement in PROC MIXED will be used to model the within subject covariance

structure. LS means along with 95% CIs by timepoint and LS mean differences between the control arm and patritumab arm along with two-sided 95% CIs for each timepoint will be derived.

For these analyses, PRO values obtained at the end of treatment visit or at any scheduled timepoint with fewer than 5 subjects in the placebo arm or patritumab arm will not be included.

Descriptive statistics for the actual value and change from baseline will be computed for the EQ-5D-5L health profile utilities and EQ-5D VAS by scheduled time of evaluation (including end of treatment visit) for all subjects and by treatment group using the EQ-5D Analysis Set. Results of the EQ VAS will be presented as a measure of overall self-rated health status.

Approved

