11.4. Mock-up Tables and Listings

The date on which the first dose of study medication (including placebo) is administered is considered as Day 1 of the study. For events occurring on or after the start of treatment, study day is calculated as the event date minus the date of first administration of study medication plus 1 day. For events occurring before the start of treatment, study day is calculated as the event date minus the date of first administration of study medication.

Raw measurements will be reported to the number of significant digits as captured electronically or on the CRF. The mean and median will be displayed to one decimal place beyond the number of decimal places the original parameter is presented, and the measure of variability (e.g., standard deviation) will be displayed to two decimal places beyond the number of decimal places the original parameter is presented. Minimums and maximums will be reported to the same number of significant digits as the parameter. Calculated percentages will be reported with 1 decimal place. When count data are presented as category frequencies and corresponding percentages, the percent will be suppressed when the count is zero. Show a 'Missing row' after the last category if there are missing observations for the variable.

P-values will be reported to 4 decimal places (SAS format pvalue6.4). Values less than 0.0001 will be displayed as <0.0001. Values greater than 0.9995 will be displayed as 1.0000. Unless otherwise indicated, 1-sided p-values are presented in the tables.

All tables will summarize data for the overall study population and by the high and low HRG expression strata. For disposition tables and safety tables the order will be overall, high, and low. For efficacy tables the order will be high, low, and overall.

Listings will be presented for each part and sorted by subject ID. When available, listings will also be sorted by study day.

Unless otherwise indicated continuous variables will be summarized using the following descriptive statistics: the number of subjects (n), mean, standard deviation, median, minimum, and maximum. The frequency and percentage of observed levels will be reported for categorical measures. Percentages will be based on the number of subjects in the relevant analysis set. All statistical analyses will be performed in SAS Version 9.1 or higher

<Run Type> (Data Cut Date: DDMMYY; Data Extraction Date: DDMMYY)

Table 15.1.1: Subject Disposition

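### ORR and the PRO model leave out the HPV randomisation stratum (and HRG when pooled), and no supportive PFS or OS model adjusts for ECOG status: a small loss that is nearly free to repair

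*SAP*

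**What the plan says.** - **Design and time-to-event analyses.** SAP 3.1 and 3.3.1 stratify randomisation by HRG and HPV. SAP 8.2.1 uses a log-rank test and Cox model stratified by HPV, plus HRG in the full analysis set (FAS). SAP 8.2.2.1 treats OS the same way.
- **ORR.** SAP 8.2.2.2: "The differences in the ORR between the control arm and patritumab arm will be presented along with two-sided 80% and 95% CIs". The formula in SAP 11.3 uses only each arm's response proportion and sample size. The SAP synopsis, on the secondary endpoints, adds "These analyses will be done using the FAS for HRG high and low strata". SAP 11.4 adds "All tables will summarize data for the overall study population and by the high and low HRG expression strata", and the shell of Table 15.2.3.1 continues to HRG low and overall.
- **PRO.** SAP 8.7.1: "The model will include treatment, time, treatment-by-time interaction, and baseline as fixed effects". There is no HPV or HRG term. The shell of Table 15.5.1.2 is repeated for HRG high, low and overall.
- **Covariates.** SAP 7.1: "No other covariate adjustments will be applied for primary and secondary efficacy analyses, except for the stratification variables if applicable". It goes on: "The PRO analyses will use baseline values of the dependent variable as a covariate in a mixed model".
- **ECOG status.** It is 0 or 1 by eligibility, summarised at baseline (SAP 8.1.3) and listed as a PFS and OS subgroup (SAP 8.2.4.2). The sensitivity analyses in SAP 8.2.1 and 8.2.4.1 cover the per-protocol set, clinical progression and a changed HRG cutoff. None adjusts for ECOG.

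**The concern.** An analysis should normally reflect the factors by which subjects were randomised. Under stratified randomisation the arms are balanced on those factors, so the true sampling variance of the ORR difference contains only within-stratum variation. A crude interval also counts the between-stratum part and so comes out too wide. Protocol 1.2 regards HPV-positive disease as having a much better prognosis and links HRG to progression and survival, so the sponsor's own reasoning favours carrying both factors into ORR.

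ECOG status is different because it is not a stratification factor. With about 35 subjects per arm in HRG-high, chance can leave the arms unequal on it, and the plan offers no adjusted hazard ratio to read beside the main one. The results are meant to guide Phase 3 design (SAP 7.5), so such a check would be useful.

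**Working it through.** **The plan's own figures.** Inputs from SAP 4: HR 0.56; 53 events, one-sided alpha 0.10 and 80% power in HRG-high; 75 events, one-sided alpha 0.05 and about 81% power in the FAS.
- Schoenfeld events: 4 × (1.2816 + 0.8416)² / (ln 0.56)² = 53.6.
- Power with 53 events: 79.6%. With 75 events: 80.7%.

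The stated figures reproduce, and nothing below alters them. The documents state no precision for ORR or PRO and give no HPV prevalence, response gap or ECOG effect, so the remaining inputs are assumptions.

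**ORR within HRG-high (35 per arm).** Stratifying by HPV removes the share π(1−π)d² / [p(1−p)] of the variance, where π is HPV-positive prevalence, d the response gap and p the overall response rate. The interval width is multiplied by √(1 − share).
- Smallest case: π = 0.10, d = 0.10, p = 0.50. Share = 0.09 × 0.01 / 0.25 = 0.0036; width −0.2%.
- Largest case: π = 0.30, d = 0.30, p = 0.35. Share = 0.21 × 0.09 / 0.2275 = 0.083; width −4.2%.
- Scale: for ORR of 50% against 35%, the SAP 11.3 formula gives a 95% interval of −0.077 to 0.355, width 0.432. The largest saving is 0.432 × 0.042 = 0.018.

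**ORR pooled over HRG.** Assume π = 0.20 for HPV, 2/3 HRG-high (70 of 105), p = 0.42, and the two factors independent with equal gap d. Share = (0.16 + 0.2222) × d² / 0.2436.

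| d | Share | Width |
|---|---|---|
| 0.10 | 0.016 | −0.8% |
| 0.20 | 0.063 | −3.2% |
| 0.30 | 0.141 | −7.3% |

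**ECOG imbalance.** With 60% ECOG 1 (assumed), the share differs between arms by 10 points or more in 39% of trials in HRG-high and 27% in the FAS. For 20 points or more the figures are 11% and 3%. A 15-point imbalance with an ECOG HR of 1.5 to 1.8 (assumed) multiplies the treatment HR by exp(0.15 × ln 1.5) = 1.06 to exp(0.15 × ln 1.8) = 1.09. That is 0.06 to 0.09 on the log scale, against a standard error of about 2/√53 = 0.27.

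**Adding ECOG as a covariate.** Simulated power for PFS in HRG-high: 70 subjects, 53 events, 20% HPV-positive with HR 0.6, 2000 runs, so a simulation error of about √(0.76 × 0.24 / 2000) = 0.9 points per figure.

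| ECOG HR | HPV-stratified Cox | Plus ECOG covariate |
|---|---|---|
| 1.0 | 78.9% | 78.5% |
| 1.5 | 75.5% | 76.6% |
| 2.0 | 75.7% | 79.3% |

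Using ECOG as an extra stratum instead lost 0.7 to 2.4 points in four of five simulated scenarios and gained 1.9 in the fifth, so a covariate is the better form.

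**PRO model.** The documents give no variance for these scores, so only the direction of the gain can be stated.

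**The case against.** The strongest reply is that little depends on this. The decision-making PFS test is stratified, as is OS. Protocol 11.7.1 calls the PRO analyses exploratory. The crude ORR interval is prespecified in Protocol 11.4.2, and its flaw here is mild conservatism. Randomisation already balances HPV and HRG, and chance imbalance in ECOG is covered by the type I error of the test. All of this stands and limits the point to an improvement.

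Four stronger readings may tempt a reader, and the documents do not support them.
- **HRG is ignored throughout.** It is not. ORR and PRO are reported separately in HRG-high and HRG-low, and SAP 8.7.1 also splits descriptive PRO summaries by HPV. Within strata the missing factor is HPV; HRG is missing only from the pooled versions.
- **SAP 7.1 forbids any adjustment.** Its restriction covers primary and secondary efficacy only and exempts the stratification variables, and it requires the baseline PRO score. A stratified ORR is already permitted. An ECOG-adjusted PFS or OS model is what it excludes.
- **An ECOG imbalance would go unseen.** The baseline tables by arm would show it, and SAP 8.2.4.2 plans PFS and OS hazard ratios within ECOG 0 and ECOG 1. What is missing is a single adjusted estimate.
- **The subgroup Cox models are deficient.** SAP 8.2.4.2 says "A Cox proportional hazards regression with treatment as the only covariate will be applied". For about 40 subjects and 29 events, stratifying by HPV and HRG raised the simulated standard error of the log HR from 0.39 to 0.41. Power at one-sided 0.05 went from 45.6% to 43.7% with no prognostic effect and from 44.5% to 44.2% with moderate effects (HPV HR 0.6, HRG HR 1.5). Only strong effects (0.4 and 2.0) gave a gain, from 36.3% to 42.3%. Table 15.2.1.1 also shows an unstratified overall HR, so the forest plot has a matching comparator.

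**Conclusion.** The point holds as a small, specific improvement. The ORR comparison omits HPV within each HRG stratum and omits both factors when pooled; the PRO model has the same omission; and no supportive PFS or OS analysis adjusts for ECOG status.

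The ORR interval is about 0.2% to 4% wider than necessary in HRG-high (at most about 0.02 on a width of 0.43) and about 1% to 7% wider in the pooled FAS. These sizes rest entirely on assumed prevalences and response gaps. The ORR point estimate should hardly move, because randomisation balances the strata. Adjusting for ECOG costs almost nothing if it is not prognostic and adds about 1 to 4 points of power if its HR is 1.5 to 2.0. A reader might infer that the primary PFS conclusion or its power is at risk; neither is.

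**What to change.** - **ORR (SAP 8.2.2.2 and 11.3).** Present a Mantel-Haenszel-weighted difference, with weights n1k × n0k / (n1k + n0k) in stratum k, and a stratified Newcombe interval. Use HPV as the stratum in HRG-high and in HRG-low, and HPV by HRG overall, with HPV coded as in the PFS analysis. Keep the crude difference as back-up: at an assumed 10% prevalence, HRG-high would hold only about 7 HPV-positive subjects across both arms.
- **PRO model (SAP 8.7.1).** Add HPV as a fixed effect, and HRG in the overall analysis. Extend the PRO sentence in SAP 7.1 to match.
- **ECOG.** Add one supportive Cox model each for PFS and OS, with the planned strata and baseline ECOG (0/1) as a covariate, and amend SAP 7.1 to allow it. The primary log-rank test stays unchanged.
- **Subgroups.** Leave the treatment-only Cox models as planned.

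The cost is SAP wording, a few program lines and extra rows in existing tables. It should be settled before unblinding, because covariates chosen afterwards carry less weight.
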